18.6 APPENDIX VI- Response Assessment for Cutaneous ALCL/Lymphomatoid Papulosis

Table 8CD30+ Lymphoproliferative Disorders (LPDs) – Recommended
Definitions of CD30+ LPDs

Response	Definition
I. Response in skin	
A. L	YP response in skin
Complete response (CR)	100% clearance of skin lesions
Partial response (PR)	50%-99% clearance of skin disease from baseline without new larger and persistent nodule(s)† in those with papular disease only
Stable disease (SD)	< 50% increase to < 50% clearance in skin disease from baseline without new larger and persistent nodule(s) in those with papular disease only
Loss of response	Increase of skin score of greater than the sum of nadir plus 50% baseline score in patients with CR or PR
Increased disease activity (IDA)*	>50% increase in skin disease from baseline without larger and persistent nodules†
Progressive disease (PD)	(1) Occurrence of larger and persistent nodule(s) (> 2 cm); and (2) extracutaneous spread
Relapse	Any disease recurrence in those with CR
B. PCALCL	response in skin
CR	100% clearance of skin lesions
PR	50%-99% clearance of skin disease from baseline without new tumors
SD	< 25% increase to < 50% clearance in skin disease from baseline
PD	$(1) \ge 25\%$ increase in skin disease from baseline; or (2) loss of response: in those with CR or PR, increase of skin score of greater than the sum of nadir plus 50% baseline score
Relapse	Any disease recurrence in those with CR
II. Nodes: response	e in lymph nodes for LYP and PCALCL‡ (peripheral and central lymph nodes)
CR	All lymph nodes are now < 1.5 cm in greatest transverse (long axis) diameter by method used to assess lymph nodes at baseline or biopsy negative for lymphoma. In addition, lymph nodes that show lymphoma involvement by biopsy and < 1.5 cm in long axis diameter at baseline must now be ≤ 1 cm in diameter of the short axis or biopsy negative for lymphoma.
PR	Cumulative reduction \geq 50% of the SPD [sum of the maximum linear dimension (major axis) × longest perpendicular dimension (minor axis)] of each abnormal lymph node at baseline and no new lymph node \geq 1.5 cm or > 1.0 cm in the short axis if long axis is 1- to 1.5-cm diameter
SD	Fails to attain the criteria for CR, PR, and PD

Page 134 of 154

LCCC1524-ATL

Administration of T lymphocytes Expressing the CD30 Chimeric Antigen Receptor (CAR) for Prevention of Relapse of CD30+ Lymphomas after High Dose Therapy and Autologous Stem Transplantation (ATLAS) ATLCAR.CD30 **Confidential**

Page 135 of 154

PD§	(1) > 50% increase in SPD from baseline of lymph nodes; or (2) any new node \geq 1.5 cm in greatest transverse diameter or > 1 cm in short axis diameter if 1- to 1.5-cm in long axis that is proven to be lymphoma histologically; or (3) loss of response: in those with PR or CR, > 50% increase from nadir in SPD of lymph nodes
Relapse	Any new lymph node \geq 1.5 cm in long axis diameter in those with CR
III. Visceral diseas	e: response in viscera for LYP and PCALCL‡
CR	Liver or spleen or any organ considered involved at baseline should not be enlarged on physical examination and should be considered normal by imaging. No nodules should be present on imaging of liver or spleen. Any posttreatment mass must be determined by biopsy to be negative for lymphoma.
PR	\geq 50% regression in any splenic or liver nodules, or in measureable disease (SPD) in any organs abnormal at baseline. No increase in size of liver or spleen and no new sites of involvement.
SD	Fails to attain the criteria for CR, PR, or PD
PD§	(1) > 50% increase in size (SPD) of any organs involved at baseline; or (2) new organ involvement; or (3) loss of response: in those with PR or CR, $> 50%$ increase from nadir in the size (SPD) of any previous organ involvement
Relapse	New organ involvement in those with CR

Skin tumor burden is assessed by counting the number of lesions before, during, and after therapeutic intervention regardless of morphology (macular, papular, or nodular; ulcerated or nonulcerated). Nodules or tumors > 2 cm should be captured separately. It may be particularly useful for the investigator to note the number of lesions in the body areas. Total body photographs offer additional help in tracking lesions and making assessments.

* The term increased disease activity (IDA) has been introduced for an increase of number of papulonodular lesions (< 2 cm), which does not imply impaired prognosis.

† Larger lesions are defined as > 2 cm in diameter. Persistent lesions are defined as lesions, which do not show spontaneous regression after 12 weeks.

‡ It is still unsolved and a matter of debate whether involvement of lymph nodes and viscera in LYP exists at all or whether the occurrence of CD30+ lymphoma in lymph nodes and viscera represents ALCL, even if clonally related to LYP. Use of FDG-PET scan in this instance is compatible with other NHLs. § Whichever criterion occurs first.

Abbreviations: CR, complete response; PR, partial response; SD, stable disease; PD, progressive disease. Reference: Blood 2011; 118:4024-4035.

Page 136 of 154

Global Response Score for LYP and PCALCL

Global Score*	Definition	Skin	Node	Viscera
LYP				
CR	Complete disappearance of all clinical evidence of disease	CR	CR or NI	NI
PR	Regression of measurable disease	CR	No CR but no PD	NI
		PR	No PD	NI
SD	Failure to attain CR, PR, or PD representative of all disease	SD or IDA (Table 19, point I)	No PD	NI
PD	Progressive disease	PD in any category	PD in any category	PD in any category
Relapse	Recurrence disease in prior CR	Relapse in any category	Relapse in any category	Relapse in any category
PCALCL				
CR	Complete disappearance of all clinical evidence of disease	CR	Both categories have CR or NI	Both categories have CR or NI
PR	Regression of measurable disease	CR	Both categories do not have a CR or NI but no PD	Both categories do not have a CR or NI but no PD
		PR	No category has a PD; and if either category is involved at baseline, at least one has a CR or PR	No category has a PD; and if either category is involved at baseline, at least one has a CR or PR
SD	Failure to attain CR, PR, or PD representative of all disease	PR	No category has a PD; and if either is involved at baseline, no CR or PR in either CR/NI, PR, OR SD in any category and neither category has a PD	No category has a PD; and if either is involved at baseline, no CR or PR in either CR/NI, PR, OR SD in any category and neither category has a PD
PD	Progressive disease	PD in any category	PD in any category	PD in any category
Relapse	Recurrence disease in prior CR	Relapse in any category	Relapse in any category	Relapse in any category

Table 9Global Response Score for LYP and PCALCL

NI indicates noninvolved

Reference: Blood 2011; 118:4024-4035.

Page 137 of 154

18.7 **APPENDIX VII - Response Assessment for Mycoses Fungoides and Sézary Syndrome**

Table 10 Modified Severity Weighted Assessment Tool for Mycoses Fungoides and Sézary Syndrome

% BSA in Body	Assessment of Involvement in Patient's Skin			
Region	Patch*	Plaque †	Tumor‡	
7				
2				
13				
8				
6				
5				
13				
5				
19				
14				
7				
1				
	×1	×2	×4	
	Region 7 2 13 8 6 5 19 14 7	Region Patch* 7	Region Patch* Plaque† 7	

Abbreviations: BSA, body surface area; mSWAT, modified Severity Weighted Assessment Tool. *Any size lesion without induration or significant elevation above the surrounding uninvolved skin; poikiloderma may be present.

†Any size lesion that is elevated or indurated; crusting, ulceration, or poikiloderma may be present. \ddagger Any solid or nodular lesion ≥ 1 cm in diameter with evidence of deep infiltration in the skin and/or vertical growth.

(Reference: Olsen EA, et al. J Clin Oncol 2011;29(18): 2598-2607)

0	A 1	1 1- 1
(on	t10	lential
con	,	onnun

Page 138 of 154

Table 11	Response in Lymph Nodes* for Mycoses Fungoides and Sézary
	Syndrome

Response	Definition
CR	All lymph nodes are now ≤ 1.5 cm in greatest transverse (long axis) diameter by method used to assess lymph nodes at baseline or biopsy negative for lymphoma; in addition, lymph nodes that were N3 classification and ≤ 1.5 cm in their long axis and > 1 cm in their short axis at baseline, must now be ≤ 1 cm in their short axis or biopsy negative for lymphoma
PR	Cumulative reduction \geq 50% of the SPD of each abnormal lymph node at baseline and no new lymph node > 1.5 cm in the diameter of the long axis or > 1.0 cm in the diameter of the short axis if the long axis is 1-1.5 cm diameter
SD	Fails to attain the criteria for CR, PR, and PD
PD†	\geq 50% increase in SPD from baseline of lymph nodes or
	Any new node > 1.5 cm in the long axis or > 1 cm in the short axis if 1-1.5 cm in the long axis that is proven to be N3 histologically or
	Loss of response: > 50% increase from nadir in SPD of lymph nodes in those with PR
Relapse	Any new lymph node > 1.5 cm in the long axis in those with CR proven to be N3 histologically

*Peripheral and central lymph nodes.

†Whichever criterion occurs first.

Abbreviations: CR, complete response; PR, partial response; SPD, sum of the maximum linear dimension (major axis) \times longest perpendicular dimension (minor axis); SD, stable disease; PD, progressive disease.

Response	Definition
CR†	B ₀
PR‡	> 50% decrease in quantitative measurements of blood tumor burden from baseline in those with high tumor burden at baseline (B ₂)
SD	Fails to attain criteria for CR, PR, or PD
PD§	B_0 to B_2 or > 50% increase from baseline and at least 5,000 neoplastic cells/µL or Loss of response: in those with PR who were originally B_2 at baseline, > 50% increase from nadir and at least 5,000 neoplastic cells/µL
Relapse	Increase of neoplastic blood lymphocytes to $\ge B_1$ in those with CR

 Table 12
 Response in Blood* for Mycoses Fungoides and Sézary Syndrome

*As determined by absolute numbers of neoplastic cells/µL.

†If a bone marrow biopsy was performed at baseline and determined to unequivocally be indicative of lymphomatous involvement, then to confirm a global CR where blood assessment now meets criteria for B0, a repeat bone marrow biopsy must show no residual disease or the response should be considered a PR only.

‡There is no PR in those with B1 disease at baseline as the difference within the range of neoplastic cells that define B1 is not considered significant and should not affect determination of global objective response.

§Whichever occurs first.
Abbreviations: CR, complete response; PR, partial response; SD, stable disease; PD, progressive disease.

(Reference: Olsen EA, et al. J Clin Oncol 2011;29(18): 2598-2607)

Page 139 of 154

Page 140 of 154

Global Score*	Definition	Skin	Nodes	Blood	Viscera
CR	Complete disappearance of all clinical evidence of disease	CR	All categories have CR/NI		
PR	Regression of measurable disease	CR	All categories do not have a CR/NI and no category has a PD		
		PR		a PD and if any c line, at least one l	
SD	Failure to attain CR, PR, or PD representative of all disease	PR	No category has a PD and if any category involved at baseline, no CR or PR in any		
		SD	CR/NI, PR, SD has a PD	in any category ar	nd no category
PD	Progressive disease		PD in any categ	ory	
Relapse	Recurrence disease in prior CR		Relapse in any c	category	

Table 13	Global Response Score for My	coses Fungoides and S	Sézary Syndrome
----------	------------------------------	-----------------------	-----------------

*It is recommended that not only the proportion of patients who achieve a response or an unfavorable outcome be calculated but a life table account for the length of the interval during which each patient is under observation also be generated.

Abbreviations: CR, complete response; NI, noninvolved; PR, partial response; PD, progressive disease; SD, stable disease.

(Reference: Olsen EA, et al. J Clin Oncol 2011;29(18): 2598-2607)

18.8 APPENDIX VIII- CRS Toxicity Grading Scale and Management Guidelines

Version 2.0 (November 2, 2017)

BACKGROUND

Immunotherapies in cancer care are becoming more widely available. As these therapies are being used more commonly, clinicians must be aware of their unique toxicities and the optimal strategies that are recommended for the management of these toxicities. One toxicity in particular associated with these immunotherapies is cytokine release syndrome (CRS). This life-threatening toxicity, if not managed both appropriately and in a timely manner, can lead to multi-organ failure and death.

Cytokine release syndrome has been observed with several different immunotherapies, including monoclonal antibodies, bi-specific antibodies, T-cell checkpoint inhibitors, and novel T-cell therapies. It is characterized by widespread activation and proliferation of lymphocytes leading to an abundant release of inflammatory cytokines well above physiologic levels. This cytokine storm can manifest in many ways from constitutional symptoms to cardiovascular and neurologic compromise. Management of this cytokine release storm involves both supportive care, and if clinically warranted, immunosuppression that blunts the aggressive cytokine response. However. administration of immunosuppressive therapies may also counter the desired immune response against targeted tumor cells. Thus, it is important that clinicians be prudent and reserve certain immunosuppressive strategies for the most appropriate clinical scenario. Thus, an algorithm that defines different grades of CRS and the corresponding therapy is necessary to guide clinicians in the delivery of appropriate care.

SIGNS/SYMPTOMS & CLINICAL GRADING

Severity of cytokine release syndrome is variable and may be influenced by tumor burden at the time of treatment with the immune-directed therapy or other pre-existing comorbidities. Clinical grading is important for appropriate management. Organ systems affected by CRS and their corresponding signs and symptoms are listed below in Table 14 and criteria for clinical grading are outlined below in Table 15.

Organ System	Signs/Symptoms
Constitutional	Fever, rigors, malaise, fatigue, anorexia, headache, myalgias/arthralgias, nausea/ vomiting
Dermatologic	Rash
Gastrointestinal	Nausea/vomiting/diarrhea
Respiratory	Tachypnea, hypoxemia (potentially requiring supplemental oxygen/ventilation)

Table 14Signs and Symptoms of CRS

Page	142	of 154	ŀ

Organ System	Signs/Symptoms
Cardiovascular	Tachycardia, hypotension
Coagulation	Disseminated intravascular coagulation (DIC) characterized by elevated D-dimer, hypofibrinogenemia, bleeding
Renal	Azotemia
Hepatic	Transaminitis, hyperbilirubinemia
Neurologic	Altered mental status, confusion, delirium, aphasia, hallucinations, tremor, seizures, ataxia

CRS Grading/Severity

The outlined clinical grading criteria, based on NCI CTCAE v4.0, is designed to guide clinicians in the management of CRS. Many of the signs and symptoms associated with CRS can also be attributable to other common complications of cancer therapy such as neutropenic fever, other infectious complications, and tumor lysis syndrome. Thus, in applying the criteria below, clinicians should exercise appropriate clinical judgement in each patient-specific scenario in an effort to distinguish true CRS from other cancer treatment-related toxicities. This will ensure appropriate delivery of care and avoidance of therapies that may otherwise not be indicated.

Page	143	of 154	

Grade 1 – Mild (Symptomatic Management)
Symptoms largely limited to constitutional symptoms listed above (Table 14)
Only requires symptomatic management
Grade 2 – Moderate (Moderate Intervention)
Hypotension responsive to fluids or single, low dose vasopressor
Oxygen requirement <40%
Grade 2 organ toxicity
Grade 3 – Severe (Aggressive Intervention)
Hypotension requiring high dose or >1 vasopressor
Oxygen requirement ≥40%
Grade 3 organ toxicity
Grade 4 transaminitis
Grade 4 – Life-threatening (Life-sustaining intervention)
Ventilator support required
Grade 4 organ toxicity, excluding transaminitis
Grade 5 – Death
Death

Table 15CRS Grading

MANAGEMENT OF CRS

MANAGEMENT OF CRS

Management of CRS involves both supportive measures and pharmacologic therapies that inhibit immune activation and amplification. Supportive measures are directed at managing constitutional symptoms and achieving and maintaining hemodynamic stability. Immune targeted therapies are directed at the cytokines released in the pathobiology of the syndrome. Cytokines identified to play a role in CRS include, but are likely not limited to, TNF α , IFNy, IL-1 β , IL-2, IL-5, IL-6, IL-8, and IL-10. Therapies utilized in CRS exhibit either a non-specific inhibition of immune amplification or a more targeted inhibition of a particular cytokine. These therapies are outlined below.

Tocilizumab

Tocilizumab is a humanized monoclonal IL-6 receptor antibody that inhibits IL-6 from binding to both cell-associated and soluble IL-6 receptors. IL-6 is a cytokine that has been implicated in the pathogenesis of CRS and presents a pharmacologic target for management. Thus, treatment strategies for CRS have focused on inhibiting IL-6 signaling.

Tocilizumab can be administered in Grade 2-4 CRS, resulting in a rapid reversal of symptoms. If there is a lack of clinical improvement, a second dose can be repeated.

Dosing:

- < 30 kg: 12 mg/kg IV over 1 hour for one dose. May repeat another 12 mg/kg dose in 8 hours if there is a lack of clinical response to the initial dose. May repeat up to 3 additional doses after the initial dose (with at least an 8 hour interval between consecutive doses).

- \geq 30 kg: 8 mg/kg IV over 1 hour for one dose (Max individual dose: 800 mg). May repeat another 8 mg/kg dose in 8 hours if there is a lack of clinical response to the initial dose (maximum of 3 additional doses after the initial dose with at least an 8 hour interval between consecutive doses).

- NOTE: Two doses of tocilizumab should be available on site for immediate use for each patient treated with CAR-T cells. These doses must be available prior to cell infusion and up to 6 weeks following cell infusion.

Corticosteroids

Steroids may be utilized in the setting of severe CRS with neurologic symptoms along with targeted cytokine therapies (i.e. tocilizumab), in severe CRS that is refractory to tocilizumab therapy, or as monotherapy for patients with isolated neurologic toxicities without systemic CRS. Steroids exhibit a non-specific immune inhibition. Intravenous dexamethasone is the preferred steroid to be initiated if steroids are warranted due to neurological symptoms given improved CNS penetration. Methylprednisolone can be used as an alternative. With appropriate response, steroids can be tapered rapidly over a few days. Dosing is as follows.

- Dexamethasone;
 - Adult: 4-10 mg (max single dose 10 mg) IV q 6 hours
 - Pediatrics: 0.1 mg/kg (max single dose 10 mg) IV q 6 hours
- Methylprednisolone
 - o Adults: 1-2 mg/kg/day IV
 - Pediatrics: 1-2 mg/kg/day IV; max daily dose 125 mg

TREATMENT ALGORITHM

Important Considerations

The following adult and pediatric treatment algorithms serve as a framework for the management of patients with CRS and are not meant to replace physician discretion. Given that each patient will require thorough clinical evaluation for proper management, an attending physician should be notified at the first signs/symptoms suggestive of CRS and should be involved in each therapeutic decision made throughout the progression of care. This includes supportive and pharmacologic interventions, as well as escalation of care from the floor to ICU-level care.

Initiation of tocilizumab and/or steroids for CRS from CAR-T therapy must be approved by one of the attendings listed in the link provided:

http://intranet.unchealthcare.org/intranet/hospitaldepartments/uncsct/cell_therapy_resourc

Signs/Symptoms	Management
Grade 1 CRS	
 Fever (≥ 38.00 C) +/- additional constitutional symptoms (rigors, malaise, fatigue, anorexia, myalgias/arthralgias, nausea/vomiting) Renal: Scr >ULN – 1.5 x ULN and/or 	 Complete infectious workup (Cultures, Chest XR/CT, etc.) Daily weights; accurate I/Os Vital signs q30 mins. until symptom resolution Initiate empiric antibiotics
 Scr 1.5 - 2.0 x above baseline and/or Scr increase > 0.3 mg/dL from baseline Hepatic: AST/ALT > ULN - 2.5 x ULN 	• Supportive measures: acetaminophen prn fevers; ondansetron or prochlorperazine prn nausea/vomiting; meperidine/morphine prn rigors

Table 16Adult CRS Treatment Algorithm

LCCC1524-ATL

Administration of T lymphocytes Expressing the CD30 Chimeric Antigen Receptor (CAR) for Prevention of Relapse of CD30+ Lymphomas after High Dose Therapy and Autologous Stem Transplantation (ATLAS) ATLCAR.CD30

R.CD30	Page 146 of 15
\circ T.bili > ULN - 1.5 x ULN	
Grade 2 CRS	
 CV: Hypotension (SBP <90 mmHg e ≥ 20% decrease in baseline SBP or DBP) +/- asymptomatic tachycardia Pulmonary: Decreased O2 saturatio (≤88%) Renal: Scr ≥ 1.5 - 3.0 x ULN and/or Scr 2.0 - 3.0 x above baseline Hepatic: AST/ALT > 2.5 - 5.0 x ULN and/or T. Bili > 1.5 - 3.0 x ULN 	 measures outlined under Grade 1 CRS Supplemental O2 up to 40% to saturation ≥93% Fluid bolus: 1000 mL IV over 1-2
Grade 3 CRS	
 CV: Hypotension (SBP <90 mmHg e ≥ 20% decrease in baseline SBP or DBP) unresponsive to fluids and low dose vasopressors given for grade 2 CRS (Table 17) +/- symptomatic tachycardia Pulmonary: Decreased O2 saturatio (≤88%) requiring >40% to achieve saturation ≥93% Neuro: Neurologic symptoms (confusion, AMS, seizure) Renal: Scr > 3.0 – 6.0 x ULN and/or 	 measures outlined under Grade 1 and 2 CRS Increase supplemental O2 to achieve saturation ≥93% High dose or multiple vasopressors (Table 17) Tocilizumab as outlined in Grade 2 CRS Dexamethasone 10 mg IV q6h if
 Scr > 3.0 x above baseline or > 4.0 	refractory to tocilizumab

LCCC1524-ATL Administration of T lymphocytes Expressing the CD30 Chimeric Antigen Receptor (CAR) for Prevention of Relapse of CD30+ Lymphomas after High Dose Therapy and Autologous Stem Transplantation (ATLAS) ATLCAR.CD30

Page	147	of 154	

 Hepatic: AST/ALT > 5.0 - 20.0 x ULN and/or T. Bili > 3.0 -10.0 x ULN Grade 4 CRS 	
 CV: Persistent hemodynamic instability (hypotension and tachycardia refractory to aggressive fluids and pressor support) Pulmonary: Hypoxic respiratory failure: O2 saturation ≥93% not able to be achieved with supplemental O2 (nasal cannula, non-rebreather) Neuro: Neurologic symptoms (confusion, AMS, seizures) Renal: Scr > 6.0 x ULN Hepatic: AST/ALT > 20.0 x ULN and/or T. Bili > 10.0 x ULN 	 Continue monitoring and supportive measures outlined in Grade 1, 2, and 3 CRS Continue/initiate vasopressors, tocilizumab, and dexamethasone as outlined in Grade 3 CRS Ventilatory support Dialysis if indicated (CVVHD or HD)

Table 17.High dose vasopressors in adult patients

Vasopressor	Dose (high dose)*
Norepinephrine	\geq 20 mcg/min monotherapy
Dopamine	$\geq 10 \text{ mcg/kg/min}$
Phenylephrine monotherapy	\geq 200 mcg/min
Epinephrine	$\geq 10 \text{ mcg/min}$
Vasopressin + additional vasopressor	Vasopressin + norepinephrine equivalent of $\geq 10 \text{ mcg/min}$

Confidential

*Vasopressors at doses lower than those outlined are considered low dose vasopressors

Table 18.Pediatric CRS Treatment Algorithm

Signs/Symptoms	Management		
Grade 1 CRS			
 Fever (≥ 38.00 C) +/- additional constitutional symptoms (rigors, malaise, fatigue, anorexia, myalgias/arthralgias, nausea/vomiting) Renal: Scr >ULN – 1.5 x ULN and/or Scr 1.5 – 2.0 x above baseline and/or Scr increase > 0.3 mg/dL from baseline Hepatic: AST/ALT > ULN – 2.5 x ULN and/or T.bili > ULN – 1.5 x ULN 	 Complete infectious workup (Cultures, Chest XR/CT, etc.) Daily weights; accurate I/Os Vital signs q30 mins. until symptom resolution Initiate empiric antibiotics Supportive measures: acetaminophen prn fevers; ondansetron or prochlorperazine prn nausea/vomiting; meperidine/morphine prn rigors 		
Grade	2 CRS		
 CV: Hypotension +/- asymptomatic tachycardia (Table 19 & Table 20) Pulmonary: Decreased O2 saturation (≤88%) 	 Continue monitoring and supportive measures outlined under Grade 1 CRS Supplemental O2 up to 40% to saturation ≥93% 		
 Renal: Scr ≥ 1.5 - 3.0 x ULN and/or Scr 2.0 - 3.0 x above baseline Hepatic: AST/ALT > 2.5 - 5.0 x ULN and/or T. Bili > 1.5 - 3.0 x ULN 	 Fluid bolus: 20 mL/kg (Max: 1000 mL) IV over 1-2 hours; Low dose vasopressor (Table 21) if unresponsive to fluid bolus Tocilizumab 		

anspl R.CI	lantation (ATLAS) D30	Page 149 of 15-
		 - <30 kg: 12 mg/kg IV over 1 hour x 1 dose; May repeat every 8 hours for a max of 3 additional doses if no improvement from initial dose - ≥30 kg: 8 mg/kg IV over 1 hour x 1 dose (Max individual dose: 800 mg); may repeat every 8 hours for a max of 3 additional doses if no improvement from initial dose
	Grade	3 CRS
•	CV: Hypotension unresponsive to fluids and low dose vasopressors given for grade 2 CRS +/- symptomatic tachycardia (Table 19 & Table 20))	• Continue monitoring and supportive measures outlined under Grade 1 and 2 CRS
•	Pulmonary: Decreased O2 saturation (≤88%) requiring >40% to achieve saturation ≥93%	 Increase supplemental O2 to achieve saturation ≥93% High dose or multiple vasopressors
•	Neuro: Neurologic symptoms (confusion, AMS, seizure)	 (Table 21) Tocilizumab as outlined in Grade 2 CRS
•	Renal: $Scr > 3.0 - 6.0 \times ULN$ and/or \circ Scr > 3.0 x above baseline or > 4.0	• Dexamethasone 0.1 mg/kg (Max 10 mg) IV q6h if neurologic symptoms
•	Hepatic: AST/ALT > 5.0 – 20.0 x ULN and/or	present or refractory to tocilizumab
	• T. Bili > $3.0 - 10.0 \text{ x ULN}$	
	Grade	4 CRS
•	CV: Persistent hemodynamic instability (hypotension and tachycardia refractory to aggressive fluids and pressor support)	• Continue monitoring and supportive measures outlined in Grade 1, 2, and 3 CRS

LCCC1524-ATL Administration of T lymphocytes Expressing the CD30 Chimeric Antigen Receptor (CAR) for Prevention of Relapse of CD30+ Lymphomas after High Dose Therapy and Autologous Stem Transplantation (ATLAS) ATLCAR.CD30

•	Pulmonary: Hypoxic respiratory failure: O2 saturation ≥93% not able to be achieved with supplemental O2 (nasal cannula, non-rebreather)	•	Continue/initiate vasopressors, tocilizumab, and dexamethasone as outlined in Grade 3 CRS Ventilatory support
•	Neuro: Neurologic symptoms (confusion, AMS, seizures)	•	Dialysis if indicated (CVVHD or HD)
•	Renal: Scr $> 6.0 \times ULN$		11 D)
•	Hepatic: AST/ALT > 20.0 x ULN and/or		
	\circ T. Bili > 10.0 x ULN		

Table 19.Definition of hypotension in pediatric patients

Age	Hypotension (SBP)
0 – 28 days	< 60 mmHg
1-12 months	< 70 mmHg
1-10 years	< 70 mmHg + (age x 2)
>10 years	< 90 mmHg

Table 20.Definition of tachycardia in pediatric patients

Age	Tachycardia (HR at Rest)	Tachycardia (HR while Awake)
0-3 months	> 160 BPM	> 205 BPM
3 months - 2 years	> 160 BPM	> 190 BPM
2-10 years	> 90 BPM	> 140 BPM
>10 years	> 90 BPM	> 100 BPM

Vasopressor	Dose (high dose)*
Norepinephrine	$\geq 2 \text{ mcg/kg/min}$
Dopamine	$\geq 10 \text{ mcg/kg/min}$
Phenylephrine monotherapy	\geq 5 mcg/kg/min
Epinephrine	$\geq 1 \text{ mcg/kg/min}$
Vasopressin	> 100 milliunits/kg/hr

Table 21.High dose vasopressors in pediatric patients

*vasopressors at doses lower than those outlined are considered low dose vasopressors

References

- 4. National Cancer Institute Common Terminology Criteria for Adverse Events v4.03; 2010. Available online at: http://evs.nci.nih.gov/ftp1/CTCAE/About.html (accessed 11/28/2015).

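### The Grade 4 CRS rows of Tables 16 and 18 include AST/ALT above 20 x ULN, which Table 15, the grading table, classes as grade 3 CRS

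*Combined protocol and SAP*

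**What the plan says.** Section 18.8 (Appendix VIII) holds both the CRS grading scale and the management guidance. Its section on signs, symptoms and clinical grading states that "criteria for clinical grading are outlined below in Table 15". Under grade 3, Table 15 lists "Grade 4 transaminitis". Under grade 4 it lists "Grade 4 organ toxicity, excluding transaminitis".

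Two treatment algorithms follow. In Table 16 (adults) the Grade 3 CRS row reads "Hepatic: AST/ALT > 5.0 - 20.0 x ULN and/or T. Bili > 3.0 -10.0 x ULN" and the Grade 4 CRS row reads "Hepatic: AST/ALT > 20.0 x ULN and/or T. Bili > 10.0 x ULN". Table 18 (pediatric) has the same transaminase entry at grade 4: "Hepatic: AST/ALT > 20.0 x ULN and/or", followed by the same bilirubin limit. The text introducing the algorithms says that they "serve as a framework for the management of patients with CRS and are not meant to replace physician discretion".

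The CRS grade is used elsewhere in the protocol:

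- Section 3.1.1 (primary endpoint) and the DLT definition in section 4.1.3 refer to the scale in section 18.8 without naming a table.
- Section 10.3.3 requires an expedited report for any CRS of grade 4 or above and names no scale.
- Section 11.3.1 tabulates the severity of each adverse event episode.
- Section 7.7 sends CRS grading to Appendix V, which contains the patient-reported outcome surveys.

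**The concern.** One appendix gives two grades for the same laboratory finding. Table 15 rejects transaminitis as a grade 4 criterion. Tables 16 and 18 accept it, and because it is joined to bilirubin by and/or, it suffices alone. Table 15 describes organ toxicity only in words, so staff looking for a numeric AST/ALT limit find it only in the algorithms, under a Grade 4 CRS heading.

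Two things are at stake. A case can fall on either side of the expedited-report threshold depending on which table is consulted. The severity recorded for the episode, and so displayed in the safety tables, can be 3 or 4.

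**Working it through.** The plan gives no figure to reproduce, so the check is a comparison of texts. Take a subject with CRS, AST/ALT at 21 x ULN and no other grade 4 feature.

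**Step 1: is this grade 4 transaminitis?** The algorithms' grade 3 band ends at 20 x ULN, and Appendix VIII says that its grading criteria are based on CTCAE v4.0. Reading values above 20 x ULN as grade 4 transaminitis is therefore an inference from the appendix itself.

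**Step 2: assign the CRS grade.**

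| Finding, as the only feature of its grade | Table 15 | Tables 16 and 18 |
|---|---|---|
| AST/ALT above 5 and up to 20 x ULN | 3 | 3 |
| AST/ALT above 20 x ULN | 3 | 4 |
| Bilirubin above 10 x ULN | 4 | 4 |

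Only the middle row conflicts. Bilirubin is consistent, because the Table 15 exclusion covers transaminitis alone.

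**Step 3: carry the grade to each place of use.**

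| Use | Grade 3 (Table 15) | Grade 4 (Tables 16 and 18) |
|---|---|---|
| Automatic expedited report, section 10.3.3 | not triggered | triggered |
| Severity of the episode, section 11.3.1 | 3 | 4 |
| DLT, section 4.1.3 | only if beyond 72 hours | only if beyond 72 hours |
| CRM and MTD, section 11.1 | unchanged | unchanged |

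The DLT row is the same because grades 3 and 4 share the 72-hour rule. The CRM takes in DLTs and not grades, so the 10% target and the 12 to 18 subjects are untouched.

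**Step 4: does treatment differ?** The grade 4 management cell says "Continue/initiate vasopressors, tocilizumab, and dexamethasone as outlined in Grade 3 CRS" and adds ventilatory support and, if indicated, dialysis. Those additions address respiratory and renal failure, which this subject does not have by assumption. Drug treatment is the same.

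**Step 5: which table should give way?** Appendix VIII names Table 15 for grading. Only Table 15 defines grade 5, which the DLT definition needs. Both algorithms show essentially the same neurologic entry at grades 3 and 4, so they cannot assign a unique grade. The Amendment 5 summary describes placing grade 4 transaminitis at grade 3 CRS as a clarification. That log is not current text, but as a sign of intent it agrees with Table 15.

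**The case against.** The strongest reply is that nothing is ambiguous. Table 15 is the only table titled as grading, the other two are titled as treatment algorithms, and the appendix calls those a management framework. The wrong reference in section 7.7 is a slip, since nobody could grade CRS from the outcome surveys, and the visit sections that cite the CRS scale (7.2.3 and 7.3.1 to 7.3.5) give Appendix VIII correctly. Grading from the algorithms would produce an extra report, which errs on the safe side. Other routes also remain. A serious, unexpected and related reaction is reportable under section 10.3.3, SAEs are recorded within 24 hours under section 10.2.2, and section 10.4 has unexpected toxicities evaluated as they occur.

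Most of this stands. A reader might infer that the trial has two competing CRS scales and that its primary endpoint is therefore undefined. The documents do not support that: Table 15 governs on any fair reading, and DLT status is the same under both.

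The reply does not remove the error in the rows. They state a numeric grade 4 threshold that the grading table expressly rejects, and the sections that use the grade do not name Table 15.

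The reply also says that one sentence of precedence would suffice and that moving hepatic entries in a versioned guideline (Version 2.0) is a clinical decision. The sentence would settle the grade formally, but it would leave the only numeric limit under the wrong heading. Moving the entries does need clinical agreement, although Step 4 shows no change in drug treatment.

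**Conclusion.** The inconsistency is in the current text, and the hepatic rows of Tables 16 and 18 are the entries in error. It matters only for CRS whose sole grade 4 feature is AST/ALT above 20 x ULN. For that case the automatic CRS report and the displayed severity of the episode depend on the table used. Nothing changes in DLT, dose assignment, the MTD or drug treatment. The point is minor.

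The conclusion rests on reading AST/ALT above 20 x ULN as grade 4 transaminitis and on the absence of any other grade 4 feature.

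Three stronger readings are not supported:

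- A reader might try to size the effect as one case over the 12 to 18 planned subjects, or from the absence of CRS among the 9 subjects in the earlier trial (section 1.5.5). Neither measures how often this case arises. The first presupposes the event. The second concerns any CRS, in a non-transplant setting without conditioning. The frequency is unknown.
- A reader might infer that a planned highest-grade CRS summary would be distorted. Section 11.3.1 plans severity by episode and no such summary.
- A reader might infer that such events would escape the FDA. They lose only the automatic CRS trigger and may still qualify as serious, unexpected and related.

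**What to change.** 1. State in Appendix VIII that Table 15 assigns the CRS grade for DLT, the safety tables and section 10.3.3 reporting, and that Tables 16 and 18 guide treatment only.
2. In Tables 16 and 18, make the grade 3 hepatic transaminase entry AST/ALT above 5 x ULN with no upper limit. Leave only bilirubin above 10 x ULN in the grade 4 hepatic entry. The grade 3 bilirubin band stays as it is.
3. In section 7.7, replace the reference to Appendix V with Appendix VIII, Table 15.

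The cost is one sentence, two hepatic entries in each of two tables (2 x 2 = 4 entries) and one cross-reference, with clinical sign-off on the guideline. No new data are needed.

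The downside is that isolated AST/ALT above 20 x ULN with CRS will no longer trigger the automatic report under any reading. If the sponsor wants those cases expedited, section 10.3.3 should name that finding explicitly.
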